1.3. Device Usage

Application of the *QuikClot® Radial®* pad will be performed by properly trained interventional cardiologists.

Application of the TR Band® will be performed by properly trained interventional cardiologists or cath lab technicians. Proper training for physicians for either device is defined as performing 2 run in procedures prior to enrolling patients in this study, supervised by a cardiologist or industry representative experienced with the either device. For cath lab technicians, proper training will be meeting the qualifications outlined by the Memorial Cardiac and Vascular Institute cath lab protocol for application of the TR Band®. [name], [name] and [name] are properly trained with the use of the *QuikClot® Radial®* pad hemostatic device and TR Band®.

1.3.1. The method for using the *QuikClot® Radial®* pad with a Coban™ Self-Adherent Wrap is as follows:

After an end-procedure ACT is drawn and the blood pressure is recorded, the arterial access sheath will be partially pulled out of the radial artery, exposing approximately 4 cm of sheath. The level of the access site will be marked on the medial and/or lateral side of the palmar surface of the wrist with a sterile marker pen so that once the pad is applied and covering the access site, the investigator will still be able to know the exact level of the access site, to properly hold pressure in the correct spot. (Fig.4A, Arrows). The *QuikClot® Radial®* pad is then applied over the access site, with the sheath still in place, with 1/3 of the pad being distal to the access site and 2/3 of the pad being proximal to the access site (Fig.4B, Arrows). The 3M™ Coban™ latex-free self-adherent wrap is then gently applied, wrapping 3-5 layers around the wrist to hold the *QuikClot® Radial®* pad in place (Fig. 4. C). When application is complete, the excess self-adherent wrap will be cut off (Fig. 4D). The 3 – 5 layers will then be hand massaged to allow the layers to adhere to each other (Fig. 4E). The sheath is then removed from the radial artery,

Fig 1. Application of the QuikClot® Radial® pad with the Coban™.

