1.6. Anticoagulation

For diagnostic cardiac catheterization using TRA in this study, a heparin dose of 70 units/kg will be used, with a minimum of 4000 units and a maximum of 7000 units. For PCI, additional heparin to attain an ACT of > 250 – 300 seconds will be used, or bivalirudin at standard FDA approved doses described in the package insert may be used at the operator’s discretion. The option of continuing a heparin or bivalirudin infusion after the PCI will be at the operator’s discretion.

2. Study Objectives

The objective of this study is to evaluate the safety and efficacy of a kaolin-based *QuikClot® Radial®* pad combined

with either a Coban™ bandage or TR Band® to achieve hemostasis after TRA, compared with ‘standard of care’ mechanical compression with the TR Band®, with the aim to hopefully develop a safe and possibly superior hemostatic method after transradial access, thus improving patient care by optimizing radial hemostasis management.

3. Study Design

[figure not shown]

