Up to now, 217 subjects have been enrolled in this trial per the previous version of this protocol, including 73 in the QuikClot®/Tegaderm™ arm, 72 in the TR Band® only arm, and 72 in the QuikClot®/Coban™ arm. This amended protocol will continue enrolling a total of 100 subjects for both the TR Band® only and the QuikClot®/Coban™ arms, respectively. The new arm 3, QuikClot®/TR Band®, will also enroll a total of 100 subjects. In this amended protocol, a total of 373 subjects will be enrolled, including the 217 that have been enrolled in the prior version of the protocol, and an additional 156 subjects enrolled in this amended protocol. Randomization of the 156 subjects in the amended protocol will continue into the 3 cohorts. As 100 subjects will be needed to fill the new Arm 3, QuikClot®/TR Band®, and only 28 subjects will be needed to fill each of Arms 1 and 2, i.e. the TR Band® and QuikClot®/Coban™ Arms, arms 1 and 2 will fill well before the new Arm 3. After Arms 1 and 2 are filled, participants assigned to Arms 1 and 2 will be considered screen failures. All screen failures in this revised protocol will be assigned into the new Arm 3, the QuikClot®/TR Band® arm. As the old arm 3 is terminated, future participants randomized into arm 3 will be considered screen failures, as our REDCap data base will consider them in the old Arm 3. All screen failures that occur during randomization in the additional 156 subjects in this revised protocol will be assigned to the new Arm 3. An example of this would be a subject randomized to Arm 1 (TR Band®) who is a diagnostic cath only, and the 50 diagnostic only cases in Arm 1 are already filled. This subject would then be assigned to new Arm 3, the QuikClot®/TR Band® arm. Another example would be a participant randomized to Arm 3. As the old Arm 3 from the prior protocol is now closed, any

subsequent participants randomized to Arm 3 will be considered screen failures, and will be assigned to the new Arm 3 of this revised protocol. Each arm of 100 patients will include 50 diagnostic-only cardiac catheterizations and 50 PCIs. Simultaneous accrual of diagnostic-only cardiac caths and PCIs will occur.

- For the TR Band®, weaning begins at the end of 60 minutes of compression and will complete over the next 60 minutes. If oozing/bleeding occurs at any point during the weaning of air, reinflation and repeat weaning will be performed per protocol.

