7.3. Sample Size and Statistics

Based on the previous study¹⁷ on the use of TR Band® and our pilot study on the *QuikClot® Radial®* pad with either a Coban™ bandage or Tegaderm™ dressing for radial hemostasis, we anticipate an average initial successful hemostasis rate of 95% or higher in patients using the *QuikClot® Radial®* pad compression device, compared to an initial successful hemostasis rate of 84% in patients using the TR Band®, and no significant differences between the two *QuikClot® Radial®* pad arms. Using a type 1 error of 0.05 for each of the two comparisons of the *QuikClot® Radial®* pad with the TR Band® and power of 80% to detect an 11% difference in the rate of initial successful hemostasis between the TR Band® arm and either *QuikClot® Radial®* pad arm, a sample size of 100 will be needed for each of the three arms of the trial. Assuming that there may be a 50% screen failure rate (patients withdraw, ulnar access is used, radial access failure, events occur during the procedure that the investigator does not wish to enter the subject or the diagnostic only cases of the study are already filled), a total of up to 600 consecutive subjects undergoing transradial diagnostic cardiac catheterization and/or PCI, who sign informed consent to participate, will be recruited into the three arms of the trial.

An interim analysis was not originally planned for the study, but was conducted after enrolling 186 participants. The results obtained from the interim analysis showed that there was a failure to obtain initial hemostasis at 5 minutes in approximately 30% of the subjects in the QuikClot®/Tegaderm™ arm of the protocol, compared to a failure to obtain initial hemostasis of 11% in the TR Band® cohort (odds ratio = 3.2, 95% CI, 1.2 – 8.1, $p = 0.013$) and a failure to obtain initial hemostasis of 8% in the QuikClot®/Coban™ cohort (odds ratio = 4.7, 95% CI, 1.7 – 12.1, $p = 0.003$). Our DSMB committee reviewed the results and recommended to stop the Tegaderm™ only arm. We here institute a new arm 3 using a QuikClot® Radial® Pad under a TR Band® with 30 minutes of compression to replace the old arm 3 in this trial. The sample size of the new arm 3 is the same as the old arm 3, with 100 participants including 50 diagnostic-only cardiac catheterizations and 50 PCIs.

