Statistical summaries and analyses of data will be performed at Memorial Healthcare System. Descriptive analysis will be performed for all data including means and standard derivation or medians for continuous variables and proportions for categorical variables. The t-test will be used to describe the differences of clinical outcomes between the two compression devices after TRA, and a two-sided p-value of 0.05 will be considered to be statistically significant.

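### Each arm is fixed at 50 diagnostic-only and 50 PCI subjects, but the only stated device comparison is unstratified; section 7.3 should stratify by procedure type and report results for each type

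*Combined protocol and SAP*

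**What the plan says.** Section 3.1 (General Design) sets the mix: "Each arm of 100 patients will include 50 diagnostic-only cardiac catheterizations and 50 PCIs". Section 7.3 repeats it for the replacement arm, "with 100 participants including 50 diagnostic-only cardiac catheterizations and 50 PCIs".

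The quota works as a cap. Section 3.1 gives the example of a diagnostic-only subject randomized to Arm 1 when "the 50 diagnostic only cases in Arm 1 are already filled"; that subject is moved to the new Arm 3. Section 7.3 also lists among its reasons for screen failure that "the diagnostic only cases of the study are already filled".

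Section 1.6 treats the two groups differently. Diagnostic cases get weight-based heparin between a stated floor and ceiling. PCI cases are described as follows: "For PCI, additional heparin to attain an ACT of > 250" (the range continues to 300 seconds). Bivalirudin is an alternative, and an infusion may continue after PCI at the operator's discretion.

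The analysis text in section 7.3 is short: "The t-test will be used to describe the differences of clinical outcomes between the two compression devices after TRA", at a two-sided 0.05 level. It has no stratum, covariate, interaction or result by procedure type. The sample size uses one success rate per device. Section 4.4 names no stratification factor for the allocation table.

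**The concern.** A design that forces equal numbers of two procedure types treats procedure type as important. The analysis then does not use it. Three things follow.

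- **Precision.** When a prognostic factor is balanced by design, a pooled standard error counts between-stratum variation that the balance has already removed. The standard error is slightly too large and the test slightly conservative.
- **Interpretation.** The pooled rate is an average over a mix chosen by quota. The pad arms end compression at about 30 minutes and the TR Band arm at 120 (section 3.2.2), while an infusion may still be running after PCI (section 1.6). Whether the short schedule holds up after PCI is a natural clinical question, and one pooled rate cannot answer it.
- **Protection.** If accrual ends with cells unfilled, procedure mix may differ between arms, and an unstratified comparison would carry that difference into the result.

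**Working it through.** **Inputs from section 7.3:** 84% success with TR Band, 95% with the pad, type 1 error 0.05 per comparison, 80% power, 100 per arm. Interim failure was 11% with TR Band and 8% with pad/Coban, so success was 89% and 92%. The 50 + 50 split is from sections 3.1 and 7.3. The documents give no radial success rates by procedure type and no natural case mix, so **every by-type rate and every mix other than 50:50 below is an assumption.**

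**1. The plan's own figure.** n = [z_α√(2p̄q̄) + 0.8416√(p₁q₁ + p₂q₂)]² / (p₂ − p₁)², with p̄ = 0.895.
- Two-sided: (1.96 × 0.4335 + 0.8416 × 0.4265)² / 0.0121 = 121 per arm.
- One-sided (1.645): 95 per arm.
- Power at 100 per arm by the same method: 72% two-sided, 82% one-sided.

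The stated 100 is therefore not reproduced under the two-sided rule. That is a separate matter and nothing below depends on it. What matters here is that the calculation has one rate per device.

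**2. Precision.** Pooled variance of the difference: Σ p(1 − p)/100 over the two arms. Stratified: 0.25 × Σ p(1 − p)/50 over the four cells. The two differ by Σ (gap between types)²/400.

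| Assumed success, diagnostic/PCI | Pooled variance (SE) | Stratified variance (SE) | Change in variance |
|---|---|---|---|
| Pad 99/91, TR Band 92/76 (averages 95 and 84) | 0.001819 (0.0426) | 0.001739 (0.0417) | −4.4% |
| Pad 98/86, TR Band 95/83 (averages 92 and 89) | 0.001715 (0.0414) | 0.001643 (0.0405) | −4.2% |

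Check on row 1: (0.08² + 0.16²)/400 = 0.00008 = 0.001819 − 0.001739. The assumed gaps are 8 and 16 points in row 1 and 12 points in both arms in row 2.

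**3. Error rate and power.** Simulation, 200,000 runs per scenario, 50 + 50 per arm. A pooled chi-square stands in for the t-test on a yes/no outcome and is compared with Cochran-Mantel-Haenszel (CMH).

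| Scenario (diagnostic/PCI) | Pooled | CMH |
|---|---|---|
| No effect, 84/84 in both arms | 5.1% | 5.0% |
| No effect, 94/74 in both arms | 4.3% | 5.0% |
| No effect, 99/69 in both arms | 3.3% | 5.0% |
| Power, TR Band 84/84, pad 95/95 | 74.8% | 74.9% |
| Power, TR Band 94/74, pad 98/92 | 75.5% | 76.2% |

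**4. Dependence on the mix.**
- If the planned 11 points were 5.5 in diagnostic cases and 16.5 in PCI, the average would be 0.7 × 5.5 + 0.3 × 16.5 = 8.8 at a 70% diagnostic share, and 0.3 × 5.5 + 0.7 × 16.5 = 13.2 at 30%.
- If effects ran in opposite directions (pad 98 v TR Band 88 in diagnostic, 86 v 90 in PCI), the average would be 0.5 × 10 − 0.5 × 4 = +3.0 at 50:50 and 0.7 × 10 − 0.3 × 4 = +5.8 at 70:30.
- If effects are equal in both types, the mix does not matter.

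**5. What 50 v 50 can show.** At 90% success, the 95% half-width is 1.96 × √(2 × 0.9 × 0.1/50) = 0.118, about 12 points. Power for 84% v 95% within one type is 43%. Interaction power for 5.5 v 16.5 points is about 25%.

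**6. Unfilled cells.** Distortion of the pooled difference = difference in diagnostic share × success gap between types. If one arm ended at 60% diagnostic and the other at 50%, with a 12-point gap, that is 0.10 × 12 = 1.2 points. Stratifying removes it.

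**The case against.** The strongest reply is that the quota does the work. With the same 50:50 split in each arm, procedure type cannot confound the device comparison, and section 3.1 calls for both types to accrue together. This stands. A reader might infer that pooling biases the result; if the quotas are met, it does not. The statistical gain is also small: a 4% variance reduction, under 1 point of power, and a pooled test that errs on the conservative side.

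Other stronger readings also fail on the documents:

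- **That the pad does worse than TR Band after PCI.** Nothing in the documents suggests it. The opposite-direction example is hypothetical, and the trial could not settle it: −4 points in PCI has SE √(0.86 × 0.14/50 + 0.90 × 0.10/50) = 0.065, so an interval of about −17 to +9.
- **That anticoagulation is the dominant influence on hemostasis.** No section says so. Section 1.1 links lack of procedural anticoagulation to radial artery occlusion. The only split by procedure type is a 40-patient femoral pilot (section 1.4, Table 2), with 4.2 minutes after diagnostic and 5.3 after interventional cases. That is indicative at most.
- **That the quota contradicts the recruitment wording in section 7.3**, "a total of up to 600 consecutive subjects undergoing transradial diagnostic cardiac catheterization and/or PCI". The same sentence lists filled diagnostic-only cases as a screen-failure reason, so the quota is disclosed there.
- **That subjects meeting a full cell are simply turned away.** Under the amendment they are mainly redirected to the new Arm 3.

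Stratifying total time will also change little, since section 3.2.2 builds in about 30 to 31 minutes for the pad arms and 120 for TR Band. Finally, the absence of a stratified analysis is read from the text; a study design figure was not available.

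What remains is that the pooled figure cannot speak to PCI separately, and that stratified power was not lower in any scenario run.

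**Conclusion.** The concern holds in a limited form. The plan balances procedure type by design and then leaves it out of its only stated comparison. With quotas met there is no bias. The cost is a variance about 4% larger than it need be (assumed gaps of 8 to 16 points), a type 1 error of 4.3% or 3.3% instead of 5% if procedure type is strongly prognostic, and a single average whose relevance depends on the mix whenever the effect differs by type. The last of these is the main reason to act. The sizes rest on assumed by-type rates; if procedure type is not prognostic and effects are equal, the loss is close to nil.

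A reader might infer that stratification would also make Arm 3 a properly randomized comparison. It would not. Redirecting screen failures to Arm 3 is a non-random route into that arm, and adjusting for procedure type removes only the part due to procedure mix.

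**What to change.** Amend section 7.3 as follows.

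1. For each pad arm against TR Band, estimate the difference in initial hemostasis as a Mantel-Haenszel risk difference stratified by procedure type (diagnostic-only, PCI), with a 95% confidence interval, and test it by CMH.
2. Include procedure type as a stratum in the analysis of total time to hemostasis.
3. Report success rates and the device difference, with 95% confidence intervals, for each procedure type. Label them descriptive and not separately powered.
4. State that the pooled figure refers to a 50:50 mix set by quota, and give the achieved cell counts by arm.

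Adjustment for end-procedure ACT is optional. Sections 1.3.1 to 1.3.3 each say "After an end-procedure ACT is drawn and the blood pressure is recorded", which states that ACT is drawn but expressly records only the blood pressure. The adjustment is feasible only if the ACT value is captured.

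The cost is a few sentences and a few lines of code, with no extra patients. Procedure type must already be known in order to run the quotas. The downside is wide by-type intervals, about ±12 points, which readers may over-interpret unless the label is clear.

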3.2. Primary Study Endpoints

3.2.1. Initial successful hemostasis: Initial successful hemostasis is defined as no evidence of external bleeding from the TRA puncture site or expanding hematoma of the forearm after completion of the above described TR Band® and *QuikClot® Radial®* pad protocols, without the need for reinflation of air in the TR Band® or reapplication of manual pressure over the *QuikClot® Radial®* pad secured with a Coban™ bandage, or use of manual compression over the arteriotomy site. If an EASY grade class 1 forearm hematoma (see below section 3.3.3) develops while either hemostatic device is in place and is successfully treated without altering the weaning protocol of either device (i.e. the need for reinflation of air upon weaning the TR Band® or manual recompression of the *QuikClot® Radial®* pad after the initial 5 minute hold), this will be considered successful hemostasis.

3.2.2. Total time to hemostasis: Total time to hemostasis will be calculated as the time needed from sheath removal to achieving complete hemostasis, as described below:

For the *QuikClot® Radial®* pad + Coban™ bandage arm, total time to hemostasis includes the initial 5

minutes of manual compression and 25 minutes of light compression with the Coban™ bandage, and plus any additional protocol directed recompression time needed to obtain complete hemostasis.

For the *QuikClot® Radial®* pad + TR band® arm, total time to hemostasis includes the initial 30 minutes of compression plus 1 minute of weaning, and any additional protocol directed recompression and/or weaning times needed to obtain complete hemostasis.

[figure not shown]
For the standard of care TR Band® arm, total time to hemostasis includes the initial 60 minutes of compression plus 60 minutes of weaning, plus any additional protocol directed recompression and/or weaning time needed to obtain complete hemostasis.

3.3. Secondary Study Endpoint

3.3.1. Radial artery occlusion (RAO): RAO will be assessed one to two hours after completed hemostasis, using the reverse Barbeau's test.²⁰ Completed hemostasis in the TR Band® cohort will be after the device is removed and the puncture site is covered with a Band-Aid or a dry gauze pad under a Tegaderm™ dressing without further bleeding/oozing from the access site or development of a forearm hematoma. Completed hemostasis in the *QuikClot® Radial®* pad/Coban™ cohort is defined as no further bleeding/oozing or development of a forearm hematoma after the Coban™ bandage is removed and the *QuikClot® Radial®* pad is secured with a Tegaderm™ dressing. Completed hemostasis in the QuikClot®/TR Band® cohort will be after the TR Band® is removed without further bleeding/oozing at the access site or development of a forearm hematoma. RAO is evaluated one to two hours after completed hemostasis based on previous findings which demonstrated the highest incidence of RAO immediately after band removal.¹¹

3.3.2. Patient comfort/pain: Patients will be asked to rate their comfort level associated with the hemostatic device they have been assigned. A verbal numeric rating scale (VNRS) will be utilized to evaluate patient comfort with each device. This scale will use a 0 to 10 numeric rating to assess overall discomfort or pain related to the access site compression with each device, where 0 indicates no discomfort or pain at all and 10 indicates the worst pain the patient can imagine. The research coordinator will review the VNRS with each patient just prior to assessment of radial artery patency with the reverse Barbeau's test.²⁰ The research coordinator will record the patient's response.

3.3.3. Access site complications: Complications related to the device will be followed up to resolution or discharge, whichever comes first. Research staff will observe and record bleeding and hematomas that occur related to the access site. The severity of bleeding and forearm hematoma will be recorded using the criteria of the Early Discharge after Transradial Stenting of Coronary Arteries (EASY) classification.²¹ See Figure below for radial artery hematoma classification. Cases of device failure, procedural difficulties, and evidence of vascular complications associated with the closure procedure will be recorded, and appropriate therapy will be given.

Radial Artery Hematoma Classification

Grade I	Grade II	Grade III	Grade IV	Grade V
• < 5 cm	• 5–10 cm	• > 10 cm	• Proximal to elbow	• Compartment syndrome
• Access site related (distal to elbow)	• Access site related (distal to elbow)	• Access site related (distal to elbow)	(nonaccess site related)	

4. Subject Selection and Withdrawal

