We were encouraged by the performance of the *QuikClot® Radial®* pad in the above small pilot studies. The small sample sizes did not allow a definitive answer as to whether reduced compression times with the *QuikClot® Radial®* pad would reliably allow significantly shorter hemostasis times allowing for earlier discharge from the hospital, lead to less RAO post procedure, or improve patient comfort. We therefore designed the first version of this larger, adequately powered, prospective randomized trial to investigate the safety and efficacy of the *QuikClot® Radial®* pad combined with either a Coban™ bandage or Tegaderm™ dressing to achieve hemostasis following TRA, compared to the standard of care TR Band®. The *QuikClot® Radial®* pad will be applied over the radial artery access site using either a Coban™ bandage or only a Tegaderm™ dressing after TRA. Then, after sheath removal, firm manual compression will be applied over the *QuikClot® Radial®* pad covered by either the Coban™ bandage or the Tegaderm™ dressing for 5 minutes, followed by 25 minutes of light compression with the Coban™ dressing in the Coban™ cohort or 25 minutes of close observation after release of manual pressure in the Tegaderm™ only cohort.

After an interim analysis of 186 subjects, and a peer data safety and monitoring board (DSMB) committee review of the results, we elected to stop the Tegaderm™ only arm. With a failure to obtain initial hemostasis at 5 minutes in approximately 30% of the subjects in this arm of the protocol, we believed there would be little chance of this Tegaderm™ only protocol being adopted clinically. There were no safety issues with the Tegaderm™ only arm, as with repeated 5 minute manual compression cycles of the *QuikClot®* pad, hemostasis was obtained in all subjects. Mean hemostasis time in the Tegaderm™ only arm was 8.1 minutes. There was just clinical futility of this arm of the protocol as written, that was not detected in the small pilot trial performed using this protocol.

A new arm 3 will replace the Tegaderm™ only arm. This new arm 3 will use a *QuikClot® Radial®* Pad under a TR Band® with 30 minutes of compression. We have a large successful anecdotal experience of using a *QuikClot® Radial®* Pad under a TR Band® with 30 minutes of compression. We and others have demonstrated that use of a hemostatic pad under a TR band® significantly shortens hemostasis time, as compared to a TR band® alone, with no increased complications noted.^[17,18]

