5.1. Visit 1 –At time of Standard of Care Cardiac Catheterization and/or PCI

All subjects will be closely monitored for bleeding from the radial artery access site. Monitoring will be continued until complete hemostasis from the radial artery has been achieved. Use of reapplication of the *QuikClot® Radial®* pad or a TR band® will be at the discretion of the investigator if hemostasis is not achieved at the end of compression period. One hour after complete hemostasis, the numeric analog pain scale will be administered and recorded by

the research coordinator, and then radial artery patency will be assessed by the research coordinator using the reverse Barbeau's test.²⁰

The research coordinator will then:

- Schedule a phone call (or bedside visit, if applicable, for those subjects still in the hospital) for Visit 2.
- Instruct the subject to call the research coordinator the day after enrollment to notify the research team of any occurrence of adverse events related to the application of either device. The subject may leave a message on the research coordinator's voicemail, if the research coordinator is not able to answer the telephone, with their condition and any adverse events. The voicemail will be checked daily. For any perceived serious adverse event by the subject, they should call the interventional cardiologist who performed the procedure or seek emergency care.

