5.2. Visit 2-One day after enrollment

For subjects who are still in the hospital, the research coordinator will visit the subjects in their hospital room the day after the procedure, to assess the subject's condition and adverse events related to application of either hemostatic device. For patients who are already at home the day after their procedure, the research coordinator will contact the subjects by telephone one day after TRA to assess the subject's condition and adverse events related to application of either hemostatic device. If it is on weekend, the research coordinator will contact the subjects by telephone the next business day. For those subjects who cannot be reached by telephone on the first attempt, the research coordinator will make three attempts, once daily, to reach the subjects.

6. Safety and Adverse Events

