6.2. Adverse Event Reporting Period

The study period during which adverse events must be reported is normally defined as the period from the initiation of any study procedures to the end of the study treatment follow-up. Only SERIOUS ADVERSE EVENTS will be reported on for this study.

Any adverse event that results in hospitalization or prolonged hospitalization should be documented and reported as a serious adverse event unless specifically instructed otherwise in this protocol. Any condition responsible for surgery should be documented as an adverse event if the condition meets the criteria for an adverse event. Neither the condition, hospitalization, prolonged hospitalization, nor surgery are reported as an adverse event in the following circumstances:

- Hospitalization or prolonged hospitalization for diagnostic or elective surgical procedures for a preexisting condition. Surgery should **not** be reported as an outcome of an adverse event if the purpose of the surgery was elective or diagnostic and the outcome was uneventful.
- Hospitalization or prolonged hospitalization required to allow efficacy measurement for the study.
- Hospitalization or prolonged hospitalization for therapy of the target disease of the study, unless it is a worsening or increase in frequency of hospital admissions as judged by the clinical investigator.

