6.3. Recording of Adverse Events

All serious adverse events occurring during the study period must be recorded. The clinical course of each event should be followed until resolution, stabilization, or until it has been determined that the study treatment or participation is not the cause. Serious adverse events that are still ongoing at the end of the study period must be followed up to determine the final outcome.

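### Non-serious access-site events first noted after a same-day discharge are asked about on day 1, but the plan does not require them to be recorded or reported by arm

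*Combined protocol and SAP*

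**What the plan says.** Access-site complications are a named secondary endpoint. Section 3.3.3 of the protocol states "Complications related to the device will be followed up to resolution or discharge, whichever comes first". It continues "Research staff will observe and record bleeding and hematomas that occur related to the access site", with severity graded on the EASY scale, and adds that vascular complications of the closure procedure are to be recorded. The two recording statements carry no time limit.

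On the day after enrollment there are two routes to further information. Section 5.1 tells the subject to call and "notify the research team of any occurrence of adverse events related to the application of either device". Section 5.2 has the research coordinator visit or telephone the subject to assess "adverse events related to application of either hemostatic device". Neither is limited to serious events.

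Section 6.2 states "Only SERIOUS ADVERSE EVENTS will be reported on for this study". Section 6.3 states "All serious adverse events occurring during the study period must be recorded" and has no matching requirement for non-serious events. Section 7.3 promises "Descriptive analysis will be performed for all data".

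**The concern.** Safety is part of the study objective (Section 2). The risks listed in Section 1.5 include skin reaction, pain and numbness, which will often be non-serious and which the EASY hematoma scale does not grade.

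The timing also matters. In all three arms something stays on the wrist until the next morning: the pad under a Tegaderm dressing in the two pad arms, and a Band-Aid or gauze in the TR Band arm (Study Summary; Sections 1.3.1, 1.3.2 and 3.1). Section 5.2 expects some subjects to be at home by then. For them, oozing or a skin reaction at removal occurs after discharge. The trial asks about such an event but gives the answer no stated place in the endpoint or the adverse event rules. The safety comparison could then omit information that the trial has already collected.

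**Working it through.** The plan gives no figure on this point to reproduce, so the check sets the sections side by side for each kind of access-site event.

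| Event | Section 3.3.3 | Sections 6.2 and 6.3 | Result |
|---|---|---|---|
| Non-serious, before discharge | Recorded, EASY-graded where applicable | Not required | Captured by the endpoint |
| Non-serious, subject still in hospital on day 1 | Recorded | Not required | Captured by the endpoint |
| Serious, at any time in the study period | Recorded if before discharge | Recorded and reported | Captured |
| Non-serious, first noted after discharge | No source named; depends on the reading | Not required | No stated destination |

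Only the last row is open, and Section 3.3.3 has two readings for it.

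1. The discharge clause ends the endpoint. The event is then outside the complication comparison as well as outside the adverse event rules.
2. The clause limits only how long a known complication is followed. The event could then be counted, but no sentence links the Visit 2 answers to the endpoint, and Sections 6.2 and 6.3 still do not require it to be recorded or reported.

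Under either reading, nothing obliges the trial to show the event by arm.

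**Size.** The documents give neither a same-day discharge fraction nor a rate of late non-serious events, so the number affected cannot be computed. As an illustration only, assume that a share p of all subjects in an arm of 100 has such an event. The expected number is 100p, and the chance of at least one is 1 − (1 − p)^100.

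| Assumed p | Expected per arm | Chance of at least one |
|---|---|---|
| 1% | 1 | 63% |
| 2% | 2 | 87% |
| 5% | 5 | 99% |
| 10% | 10 | over 99.9% |

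**Subjects already enrolled.** Section 3.1 gives 217, of whom 73 were in the closed Tegaderm-only arm: 217 − 73 = 144 in retained arms, 72 in the TR Band arm and 72 in the pad + Coban arm.

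**The case against.** The best defence is that Section 3.3.3 does not close at discharge. Resolution can apply only to a complication that already exists, so the clause most naturally sets how long a known event is followed, and the recording sentences have no time limit. This is a fair reading, and it is why the point cannot be put as a definite exclusion from the endpoint. It does not settle the matter, because the section still names no source for events that arise at home.

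A second defence is that Section 6.2 concerns reporting to outside bodies, that Section 6.3 does not forbid recording other events, and that Section 7.3 covers all data. It is true that no sentence says the day 1 answers go unrecorded. But reporting to the IRB and the funding sponsor has its own Section 6.4, Section 6.2 speaks of what is reported on for the study, and the Section 7.3 sentence lists summary statistics without saying which events must be collected. What remains is an absence of any requirement, not a prohibition.

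A reader might also infer that the arms are observed for unequal times and that the comparison is therefore biased, since Section 1.1 hopes for "significantly shorter hemostasis times allowing for earlier discharge from the hospital". The documents do not show this. Discharge is not tied to hemostasis time. In the pilot table in Section 1.4, mean compression differed by 149.4 − 30.7 = 118.7 minutes between the TR Band and the 30-minute pad group, while mean recovery-unit time differed by only 263.3 − 238.9 = 24.4 minutes and was reported as not significant. With 10 subjects per group this is imprecise, and recovery-unit time is not discharge time, but it gives no support to a claim of differential bias.

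**Conclusion.** The concern holds in a limited form. The plan asks every subject about device-related events of any severity on day 1, yet has no rule requiring a non-serious access-site event first noted after a same-day discharge to be recorded or shown by arm. Whether such an event counts toward the secondary endpoint depends on which reading of Section 3.3.3 is taken.

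Two stronger inferences are not supported. The serious-only rule does not remove non-serious events from the endpoint in general: a small hematoma seen before discharge is recorded under Section 3.3.3. Nor can a bias between arms be claimed, in size or in direction.

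Severity is low. The primary endpoints are not touched, and the gap concerns one class of event. The conclusion rests on the wording of the sections and on the expectation in Section 5.2 that some subjects are at home on day 1. The percentages illustrated above are assumptions and carry no weight in it.

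**What to change.** 1. In Sections 6.2 and 6.3, exempt device-related access-site events from the serious-only rule. Those of any severity learned of at Visit 2 should be recorded with their date of onset and tabulated by arm. The serious-only rule can stay for other events.
2. In Section 3.3.3, state that access-site complications with onset from sheath removal through the calendar day after the procedure count in all arms, regardless of discharge and of when the contact is made. Report by arm how many subjects were not reached. The window should be defined by onset and not by the contact itself, because Section 5.2 moves weekend contacts to the next business day and allows three once-daily attempts.
3. Present staff-observed, EASY-graded events before discharge separately from self-reported events after it, and treat the latter descriptively. Use whatever Visit 2 records exist for the 144 subjects already enrolled in the retained arms, and state by arm how many have a usable record. Disclose that the change followed the unplanned interim analysis described in Section 7.3.

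The cost is some wording and a few data fields, since the day 1 contact already takes place. The limits should be stated with the results. Post-discharge events are self-reports in an open-label trial and cannot be reliably EASY-graded. A contact made early on day 1 cannot cover the rest of that day. Earlier records may be incomplete, and all 144 of them are in the TR Band and pad + Coban arms. The change also alters the stated scope of a secondary endpoint partway through the trial.
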